9.6. CTCAE Based Laboratory Test Results Grading Specifications

Lab Test = Albumin

CTCAE Term	Grade 1	Grade 2	Grade 3	Grade 4	Grade 5
Hypoalbuminemia	<lln -="" 3="" dl;
<lln -="" 30="" g="" l<="" td=""><3 - 2 g/dL; <30 - 20 g/L	<2 g/dL; <20 g/L	Life-threatening consequences; urgent intervention indicated	Death	</lln></lln>	<3 - 2 g/dL; <30 - 20 g/L	<2 g/dL; <20 g/L	Life-threatening consequences; urgent intervention indicated	Death

Albumin will have grades 1-3,

- Grade 1 being any values from the LLN to 3 g/dL,
- Grade 2 from 2 to < 3 g/dL and
- Grade 3 < 2 g/dL

Lab Test = Amylase

CTCAE Term	Grade 1	Grade 2	Grade 3	Grade 4	Grade 5
Serum amylase increased	>ULN - 1.5 x ULN	>1.5 - 2.0 x ULN; >2.0 - 5.0 x ULN and asymptomatic	>2.0 - 5.0 x ULN with signs or symptoms; >5.0 x ULN and asymptomatic	>5.0 x ULN and with signs or symptoms	-

Amylase will have Grades 1, 2 and 3:

- Grade 1 being any values from the ULN to 1.5 x ULN
- Grade 2 from >1.5 to 5.0 x ULN
- Grade 3 from>5 x ULN

Lab Test = Alkaline Phosphatase

CTCAE Term	Grade 1	Grade 2	Grade 3	Grade 4	Grade 5
Alkaline phosphatase increased	baseline was normal;	>2.5 - 5.0 x ULN if baseline was normal; >2.5 - 5.0 x baseline if baseline was abnormal	>5.0 - 20.0 x ULN if baseline was normal; >5.0 - 20.0 x baseline if baseline was abnormal	>20.0 x ULN if baseline was normal; >20.0 x baseline if baseline was abnormal	-

Alkaline Phosphatase will have grades 1-4 and grading is based ULN only.

- Grade 1 being any values from the ULN to 2.5 x ULN
- Grade 2 from >2.5 to 5.0 x ULN
- Grade 3 from >5.0 to 20.0 x ULN
- Grade 4 from>20.0 x ULN

Lab Test = Alanine Aminotransferase

CTCAE Term	Grade 1	Grade 2	Grade 3	Grade 4	Grade 5
Alanine aminotransferase increased	baseline was normal;	>3.0 - 5.0 x ULN if baseline was normal; >3.0 - 5.0 x baseline if baseline was abnormal	>5.0 - 20.0 x ULN if baseline was normal; >5.0 - 20.0 x baseline if baseline was abnormal	>20.0 x ULN if baseline was normal; >20.0 x baseline if baseline was abnormal	-

ALT will have grades 1-4 and grading is based ULN only.

- Grade 1 being any values from the ULN to 3.0 x ULN
- Grade 2 from >3.0 to 5.0 x ULN
- Grade 3 from >5.0 to 20.0 x ULN
- Grade 4 from>20.0 x ULN

Lab Test = Aspartate Aminotransferase

CTCAE Term	Grade 1	Grade 2	Grade 3	Grade 4	Grade 5
Aspartate aminotransferase increased	baseline was normal;	>3.0 - 5.0 x ULN if baseline was normal; >3.0 - 5.0 x baseline if baseline was abnormal	>5.0 - 20.0 x ULN if baseline was normal; >5.0 - 20.0 x baseline if baseline was abnormal	>20.0 x ULN if baseline was normal; >20.0 x baseline if baseline was abnormal	-

AST will have grades 1-4 and grading is based ULN only.

- Grade 1 being any values from the ULN to 3.0 x ULN
- Grade 2 from >3.0 to 5.0 x ULN
- Grade 3 from >5.0 to 20.0 x ULN
- Grade 4 from>20.0 x ULN

Lab Test = Bilirubin

CTCAE Term	Grade 1	Grade 2	Grade 3	Grade 4	Grade 5
Blood bilirubin increased		>1.5 - 3.0 x ULN if baseline was normal; >1.5 - 3.0 x baseline if baseline was abnormal	>3.0 - 10.0 x ULN if baseline was normal; >3.0 - 10.0 x baseline if baseline was abnormal	>10.0 x ULN if baseline was normal; >10.0 x baseline if baseline was abnormal	-

Bilirubin will have grades 1-4 and grading is based ULN only

- Grade 1 being any values from the ULN to 1.5 x ULN
- Grade 2 from >1.5 to 3.0 x ULN
- Grade 3 from >3.0 to 10.0 x ULN
- Grade 4 from>10.0 x ULN

CTCAE Term	Grade 1	Grade 2	Grade 3	Grade 4	Grade 5
Hypocalcemia	Corrected serum calcium of <lln -
8.0 mg/dL; <lln -
2.0 mmol/L; Ionized calcium <lln -="" 1.0
mmol/L</lln></lln></lln>	Corrected serum calcium of <8.0 - 7.0 mg/dL; <2.0 - 1.75 mmol/L; Ionized calcium <1.0 - 0.9 mmol/L; symptomatic	Corrected serum calcium of <7.0 - 6.0 mg/dL; <1.75 - 1.5 mmol/L; Ionized calcium <0.9 - 0.8 mmol/L; hospitalization indicated	Corrected serum calcium of <6.0 mg/dL; <1.5 mmol/L; Ionized calcium <0.8 mmol/L; life-threatening consequences	Death
Hypercalcemia	Corrected serum calcium of >ULN - 11.5 mg/dL; >ULN - 2.9 mmol/L; Ionized calcium >ULN - 1.5 mmol/L	Corrected serum calcium of >11.5 - 12.5 mg/dL; >2.9 - 3.1 mmol/L; Ionized calcium >1.5 - 1.6 mmol/L; symptomatic	Corrected serum calcium of >12.5 - 13.5 mg/dL; >3.1 - 3.4 mmol/L; Ionized calcium >1.6 - 1.8 mmol/L; hospitalization indicated	Corrected serum calcium of >13.5 mg/dL; >3.4 mmol/L; Ionized calcium >1.8 mmol/L; life-threatening consequences	Death

Lab Test = Corrected Serum Calcium

Calcium will have to be corrected for albumin using Payne's formula:

Corrected calcium = measured Ca (mg/dL) + $0.8 \times (4.0 \text{ g/dL} - \text{patient albumin (g/dL)})$.

(NOTE: It should be confirmed with the lab whether or not the correction has already been applied).

The grading is in both directions High and Low. Both directions are graded in 4 categories as Hypercalcemia

- Grade 1 being any values from the ULN to 11.5 mg/dL,
- Grade 2 from >11.5 to 12.5 mg/dL,
- Grade 3 from >12.5 to 13.5 mg/dL,
- Grade 4 >13.5 mg/dL

Hypocalcemia

- Grade 1 being any values from the LLN to 8.0 mg/dL,
- Grade 2 from 7.0 to <8.0 mg/dL,
- Grade 3 from 6.0 to <7.0 mg/dL,
- Grade 4 <6.0 mg/dL

Lab Test = Cholesterol

CTCAE Term	Grade 1	Grade 2	Grade 3	Grade 4	Grade 5
Cholesterol high	>ULN - 300 mg/dL; >ULN - 7.75 mmol/L	>300 - 400 mg/dL; >7.75 - 10.34 mmol/L	>400 - 500 mg/dL; >10.34 - 12.92 mmol/L	>500 mg/dL; >12.92 mmol/L	-

Cholesterol will have grades 1-4,

- Grade 1 being any values from the ULN to 300 mg/dL,
- Grade 2 from >300 to 400 mg/dL,
- Grade 3 from >400 to 500 mg/dL,
- Grade 4 >500 mg/dL

Lab Test = Creatine Kinase

CTCAE Term	Grade 1	Grade 2	Grade 3	Grade 4	Grade 5
CPK increased	>ULN - 2.5 x ULN	>2.5 x ULN - 5 x ULN	>5 x ULN - 10 x ULN	>10 x ULN	-

Creatine Kinase will have grades 1-4,

- Grade 1 being any values from the ULN to 2.5 x ULN,
- Grade 2 from >2.5 to 5 x ULN,
- Grade 3 from >5 to 10 x ULN,
- Grade 4 >10 ULN

Lab Test = Creatinine

CTCAE Term	Grade 1	Grade 2	Grade 3	Grade 4	Grade 5
Creatinine increased	>ULN - 1.5 x ULN	>1.5 - 3.0 x baseline; >1.5 - 3.0 x ULN	>3.0 x baseline; >3.0 - 6.0 x ULN	>6.0 x ULN	-

Creatinine will have grades 1-4

- Grade 1 being any values from the ULN to 1.5 x ULN,
- Grade 2 from >1.5 to 3.0 x ULN or >1.5 3.0 x baseline,
- Grade 3 from >3.0 to 6.0 x ULN or >3.0 x baseline,
- Grade 4 >6.0 x ULN

Lab Test = Fibrinogen

CTCAE Term	Grade 1	Grade 2	Grade 3	Grade 4	Grade 5
Fibrinogen decreased	<1.0 - 0.75 x LLN; if abnormal, <25% decrease from baseline	<0.75 - 0.5 x LLN; if abnormal, 25 - <50% decrease from baseline	<0.5 - 0.25 x LLN; if abnormal, 50 - <75% decrease from baseline	<0.25 x LLN; if abnormal, 75% decrease from baseline; absolute value <50 mg/dL	-

Fibrinogen will have Grades 1-4:

- Grade 1 <1.0 0.75 x LLN
- Grade 2 <0.75 0.5 x LLN
- Grade 3 < 0.5 0.25 x LLN
- Grade 4 < 0.25 x LLN

Lab Test = Gamma-Glutamyl Transpeptidase

CTCAE Term	Grade 1	Grade 2	Grade 3	Grade 4	Grade 5
GGT increased		>2.5 - 5.0 x ULN if baseline was normal; >2.5 - 5.0 x baseline if baseline was abnormal	>5.0 - 20.0 x ULN if baseline was normal; >5.0 - 20.0 x baseline if baseline was abnormal	>20.0 x ULN if baseline was normal; >20.0 x baseline if baseline was abnormal	-

Gamma-Glutamyl Transpeptidase will have grades 1-4 and based on ULN only

- Grade 1 being any values from the ULN to 2.5 x ULN,
- Grade 2 from >2.5 to 5.0 x ULN
- Grade 3 from >5.0 to 20.0 x ULN
- Grade 4 from>20.0 x ULN

Lab Test = Glucose

CTCAE Term	Grade 1	Grade 2	Grade 3	Grade 4	Grade 5
Hyperglycemia	Abnormal glucose above baseline with no medical intervention	Change in daily management from baseline for a diabetic; oral antiglycemic agent initiated; workup for diabetes	Insulin therapy initiated; hospitalization indicated	Life-threatening consequences; urgent intervention indicated	Death
Hypoglycemia	<lln -="" 55="" dl;
<lln -="" 3.0="" l<="" mmol="" td=""><55 - 40 mg/dL; <3.0 - 2.2 mmol/L	<40 - 30 mg/dL; <2.2 - 1.7 mmol/L	<30 mg/dL; <1.7 mmol/L; life- threatening consequences; seizures	Death	</lln></lln>	<55 - 40 mg/dL; <3.0 - 2.2 mmol/L	<40 - 30 mg/dL; <2.2 - 1.7 mmol/L	<30 mg/dL; <1.7 mmol/L; life- threatening consequences; seizures	Death

Hypoglycemia will have grades 1-4,

- Grade 1 being any values from the LLN to 55 mg/dL,
- Grade 2 from 40 to <55 mg/dL,
- Grade 3 from 30 to <40 mg/dL,
- Grade 4 <30 mg/dL

Hyperglycemia will have one grade using the WHO criterion below

• Grade 1 >200 mg/dL;

Lab Test = Lipase

CTCAE Term	Grade 1	Grade 2	Grade 3	Grade 4	Grade 5
Serum lipase increased	>ULN - 1.5 x ULN	>1.5 - 2.0 x ULN; >2.0 - 5.0 x ULN and asymptomatic	>2.0 - 5.0 x ULN with signs or symptoms; >5.0 x ULN and asymptomatic	>5.0 x ULN and with signs or symptoms	-

Lipase will have Grades 1, 2 and 3:

- Grade 1 being any values from the ULN to 1.5 x ULN
- Grade 2 from >1.5 to 5.0 x ULN
- Grade 3 from>5 x ULN

Lab Test = Magnesium

CTCAE Term	Grade 1	Grade 2	Grade 3	Grade 4	Grade 5
Hypermagnesemia	>ULN - 3.0 mg/dL; >ULN - 1.23 mmol/L	-	>3.0 - 8.0 mg/dL; >1.23 - 3.30 mmol/L	>8.0 mg/dL; >3.30 mmol/L; life- threatening consequences	Death
Hypomagnesemia	<lln -="" 1.2="" dl;
<lln -="" 0.5="" l<="" mmol="" td=""><1.2 - 0.9 mg/dL; <0.5 - 0.4 mmol/L	<0.9 - 0.7 mg/dL; <0.4 - 0.3 mmol/L	<0.7 mg/dL; <0.3 mmol/L; life- threatening consequences	Death	</lln></lln>	<1.2 - 0.9 mg/dL; <0.5 - 0.4 mmol/L	<0.9 - 0.7 mg/dL; <0.4 - 0.3 mmol/L	<0.7 mg/dL; <0.3 mmol/L; life- threatening consequences	Death

Hypermagnesemia will have grades 1, 3, and 4,

- Grade 1 being any values from the ULN to 3.0 mg/dL,
- Grade 3 from >3.0 to 8.0 mg/dL,
- Grade 4 from>8.0 mg/dL

Hypomagnesemia will have grades 1 - 4,

- Grade 1 being any values from the LLN to 1.2 mg/dL,
- Grade 2 from 0.9 to <1.2 mg/dL,
- Grade 3 from 0.7 to <0.9 mg/dL,
- Grade 4 <0.7 mg/dL

Lab Test = Potassium

CTCAE Term	Grade 1	Grade 2	Grade 3	Grade 4	Grade 5
Hyperkalemia	>ULN - 5.5 mmol/L	>5.5 - 6.0 mmol/L; intervention initiated	>6.0 - 7.0 mmol/L; hospitalization indicated	>7.0 mmol/L; life- threatening consequences	Death
Hypokalemia	<lln -="" 3.0="" l<="" mmol="" td="">Symptomatic with <lln -
3.0 mmol/L; intervention indicated</lln>	<3.0 - 2.5 mmol/L; hospitalization indicated	<2.5 mmol/L; life- threatening consequences	Death	</lln>	Symptomatic with <lln -
3.0 mmol/L; intervention indicated</lln>	<3.0 - 2.5 mmol/L; hospitalization indicated	<2.5 mmol/L; life- threatening consequences	Death

Hyperkalemia will have grades 1-4,

- Grade 1 being any values from the ULN to 5.5 mmol/L,
- Grade 2 from >5.5 to 6.0 mmol/L,
- Grade 3 from >6.0 to 7.0 mmol/L,
- Grade 4 from>7.0 mmol/L

Hypokalemia will have grades 1, 3, and 4,

- Grade 1 being any values from the LLN to 3.0 mmol/L,
- Grade 3 from >2.5 to 3.0 mmol/L,
- Grade 4 <2.5 mmol/L

Lab Test = Sodium

CTCAE Term	Grade 1	Grade 2	Grade 3	Grade 4	Grade 5
Hypernatremia	>ULN - 150 mmol/L	>150 - 155 mmol/L; intervention initiated	>155 - 160 mmol/L; hospitalization indicated	>160 mmol/L; life- threatening consequences	Death
Hyponatremia	<lln -="" 130="" l<="" mmol="" td="">125-129 mmol/L and asymptomatic	125-129 mmol/L symptomatic; 120-124 mmol/L regardless of symptoms	<120 mmol/L; life- threatening consequences	Death	</lln>	125-129 mmol/L and asymptomatic	125-129 mmol/L symptomatic; 120-124 mmol/L regardless of symptoms	<120 mmol/L; life- threatening consequences	Death

Hypernatremia will have grades 1-4,

- Grade 1 being any values from the ULN to 150 mmol/L,
- Grade 2 from >150 to 155 mmol/L,
- Grade 3 from >155 to 160 mmol/L,
- Grade 4 from>160 mmol/L

Hyponatremia will have grades 1-4,

- Grade 1 being any values from the LLN to 130 mmol/L,
- Grade 2 from 125 to <130 mmol/L,
- Grade 3 from 120 to <125 mmol/L,
- Grade 4 <120 mmol/L

Lab Test = Triglycerides

CTCAE Term	Grade 1	Grade 2	Grade 3	Grade 4	Grade 5
Hypertriglyceridemia	150 mg/dL - 300 mg/dL; 1.71 mmol/L - 3.42 mmol/L	.	>500 mg/dL - 1000 mg/dL; >5.7 mmol/L - 11.4 mmol/L	>1000 mg/dL; >11.4 mmol/L; life- threatening consequences	Death

Triglycerides will have grades 1-4,

- Grade 1 being any values from the 150 to 300 mg/dL,
- Grade 2 from >300 to 500 mg/dL,
- Grade 3 from >500 to 1000 mg/dL,
- Grade 4 from>1000 mmol/L

Lab Test = Uric Acid

CTCAE Term	Grade 1	Grade 2	Grade 3	Grade 4	Grade 5
Hyperuricemia	>ULN without physiologic consequences	-	>ULN with physiologic consequences	Life-threatening consequences	Death

Uric Acid will not be CTCAE graded.

Lab Test = Bicarbonate or CO2

CTCAE Term	Grade 1	Grade 2	Grade 3	Grade 4	Grade 5
Blood bicarbonate decreased	<lln and="" initiated<="" intervention="" no="" td="">-	-	-	-	</lln>	-	-	-	-

Bicarbonate or CO2 will not be CTCAE graded.

Lab Test = Phosphorus or Phosphate

CTCAE Term	Grade 1	Grade 2	Grade 3	Grade 4	Grade 5
Hypophosphatemia	Laboratory finding only and intervention not indicated	Oral replacement therapy indicated	Severe or medically significant but not immediately life-threatening; hospitalization or prolongation of existing hospitalization indicated	Life-threatening consequences	Death
Hyperphosphatemia	Laboratory finding only and intervention not indicated	Noninvasive intervention indicated	Severe or medically significant but not immediately life-threatening; hospitalization or prolongation of existing hospitalization indicated	Life-threatening consequences; urgent intervention indicated (e.g., dialysis)	Death

Phosphorus or Phosphate will not be CTCAE graded.

Lab Test = Serum pH [This is not urine pH]

CTCAE Term	Grade 1	Grade 2	Grade 3	Grade 4	Grade 5
Acidosis	pH <normal, but
>=7.3</normal,>	-	pH <7.3	Life-threatening consequences	-
Alkalosis	pH >normal, but <=7.5	-	pH >7.5	Life-threatening consequences	-

Serum pH will be graded in both directions with Grades 1 and 3 only.

Acidosis Grade 1 .<LLN, but >=7.3 Grade 3, pH < 7.3

Alkaosis Grade 1 .>ULN, but <=7.5 Grade 3, pH < 7.5

Lab Test = Activated Partial Thromboplastin Time

CTCAE Term	Grade 1	Grade 2	Grade 3	Grade 4	Grade 5
Activated partial thromboplastin time prolonged	>ULN - 1.5 x ULN	>1.5 - 2.5 x ULN	>2.5 x ULN; bleeding	-	-

APTT will be graded in Grade 1-3

- Grade 1 being any values from the >ULN to 1.5 x ULN,
- Grade 2 from >1.5 to 2.5 x ULN,
- Grade 3 from >2.5 x ULN,

Lab Test = International Normalized Ratio

CTCAE Term	Grade 1	Grade 2	Grade 3	Grade 4	Grade 5
INR increased	>1.2 - 1.5; >1 - 1.5 x baseline if on anticoagulation; monitoring only indicated	>1.5 - 2.5; >1.5 - 2.5 x baseline if on anticoagulation; dose adjustment indicated	>2.5; >2.5 x baseline if on anticoagulation; bleeding	-	-

INR will be graded in Grade 1-3 without baseline factor

- Grade 1 being any values from the >1.2 to 1.5,
- Grade 2 from >1.5 to 2.5,
- Grade 3 from >2.5,

Lab Test = Eosinophils

CTCAE Term	Grade 1	Grade 2	Grade 3	Grade 4	Grade 5
Eosinophilia	>ULN and >Baseline	-	Steroids initiated	-	-

Eosinophils will not be CTCAE graded

Lab Test = Hemoglobin

CTCAE Term	Grade 1	Grade 2	Grade 3	Grade 4	Grade 5
Anemia	Hemoglobin (Hgb) <lln -="" 10.0="" dl;
<lln -="" 6.2="" l;
<lln -="" 100="" g="" l<="" td="">Hgb <10.0 - 8.0 g/dL; <6.2 - 4.9 mmol/L; <100 - 80g/L	Hgb <8.0 g/dL; <4.9 mmol/L; <80 g/L; transfusion indicated	Life-threatening consequences; urgent intervention indicated	Death	</lln></lln></lln>	Hgb <10.0 - 8.0 g/dL; <6.2 - 4.9 mmol/L; <100 - 80g/L	Hgb <8.0 g/dL; <4.9 mmol/L; <80 g/L; transfusion indicated	Life-threatening consequences; urgent intervention indicated	Death
Hemoglobin Increased	Increase in > 0-2	Increase in >2-4g/dL	Increase > 4 g/DL	-	Death

Decreased Hemoglobin will have grades 1-3, with

- Grade 1 being any values from the LLN to 10 g/DL,
- Grade 2 from 8 to < 10 g/DL and
- Grade 3 < 8 g/DL

Increased Hemoglobin will not be graded.

Lab Test = CD4 Lymphocytes

CTCAE Term	Grade 1	Grade 2	Grade 3	Grade 4	Grade 5
CD4 lymphocytes decreased	<lln -="" 500="" mm3;
<lln -="" 0.5="" 10e9
/L</lln></lln>	<500 - 200/mm3; <0.5 - 0.2 x 10e9 /L	<200 - 50/mm3; <0.2 x 0.05 - 10e9 /L	<50/mm3; <0.05 x 10e9 /L	-

Decreased CD4 count will have grades 1-4, with

- Grade 1 being any values from the LLN to 500/mm3,
- Grade 2 from <500 to 200/mm3 and
- Grade 3 from <200 to 50/mm3 and
- Grade 4 <50/mm3

Lab Test = Lymphocytes

CTCAE Term	Grade 1	Grade 2	Grade 3	Grade 4	Grade 5
Lymphocyte count decreased	<lln -="" 800="" mm3;
<lln -="" 0.8="" 10e9="" l<="" td="" x=""><800 - 500/mm3; <0.8 - 0.5 x 10e9 /L	<500 - 200/mm3; <0.5 - 0.2 x 10e9 /L	<200/mm3; <0.2 x 10e9 /L	Lymphocyte count decreased	</lln></lln>	<800 - 500/mm3; <0.8 - 0.5 x 10e9 /L	<500 - 200/mm3; <0.5 - 0.2 x 10e9 /L	<200/mm3; <0.2 x 10e9 /L	Lymphocyte count decreased
Lymphocyte count increased	-	>4000/mm3 - 20,000/mm3	>20,000/mm3	-	Lymphocyte count increased

Decreased Lymphocytes will have grades 1-4, with

- Grade 1 being any values from the LLN to 800/mm3,
- Grade 2 from <800 to 500/mm3 and
- Grade 3 from <500 to 200/mm3 and
- Grade 4 <200/mm3

Increase Lymphocytes will have grades 2 and 3 only, with

- Grade 2 from >4000 to 20,000/mm3 and
- Grade 3 >20,000/mm3

Lab Test = Neutrophils

CTCAE Term	Grade 1	Grade 2	Grade 3	Grade 4	Grade 5
Neutrophil count decreased	<lln -="" 1500="" mm3;
<lln -="" 1.5="" 10e9
/L</lln></lln>	<1500 - 1000/mm3; <1.5 - 1.0 x 10e9 /L	<1000 - 500/mm3; <1.0 - 0.5 x 10e9 /L	<500/mm3; <0.5 x 10e9 /L	-

Neutrophils will have grades 1-4, with

- Grade 1 being any values from the LLN to 1500/mm3,
- Grade 2 from 1000 to <1500/mm3 and
- Grade 3 from 500 to <1000/mm3 and
- Grade 4 <500/mm3

Lab Test = Platelets

CTCAE Term	Grade 1	Grade 2	Grade 3	Grade 4	Grade 5
Platelet count decreased	<lln -
75,000/mm3; <lln - 75.0 x 10e9 /L</lln </lln>	<75,000 - 50,000/mm3; <75.0 - 50.0 x 10e9 /L	<50,000 - 25,000/mm3; <50.0 - 25.0 x 10e9 /L	<25,000/mm3; <25.0 x 10e9 /L	-

Platelet count will not be CTCAE graded

Lab Test = WBC

CTCAE Term	Grade 1	Grade 2	Grade 3	Grade 4	Grade 5
White blood cell decreased	<lln -="" 3000="" mm3;
<lln -="" 10e9
/L</lln></lln>	<3000 - 2000/mm3; <3.0 - 2.0 x 10e9 /L	<2000 - 1000/mm3; <2.0 - 1.0 x 10e9 /L	<1000/mm3; <1.0 x 10e9 /L	-
Leukocytosis	-	-	>100,000/mm3	Clinical manifestations of leucostasis; urgent intervention indicated	Death

Decreased WBC will have grades 1-4, with

- Grade 1 being any values from the LLN to 3000/mm3,
- Grade 2 from 2000 to <3,000/mm3 and
- Grade 3 from 1000 to <2,000/mm3 and
- Grade 4 <1000/mm3

High WBC will have grade 1, with

• Grade 1 >11,000/mm3 (https://www.aafp.org/afp/2000/1101/p2053.html),

Lab Test = Urine Glucose

CTCAE Term	Grade 1	Grade 2	Grade 3	Grade 4	Grade 5
Glucosuria	Present	-	-	-	-

Urine Glucose will have grades 1,

• Grade 1 if not negative or trace

Lab Test = Urine Protein

CTCAE Term	Grade 1	Grade 2	Grade 3	Grade 4	Grade 5
Proteinuria	1+ proteinuria; urinary protein ≥ULN - <1.0 g/24 hrs	Adult: 2+ and 3+ proteinuria; urinary protein 1.0 - <3.5 g/24 hrs; Pediatric: Urine P/C (Protein/Creatinine) ratio 0.5 - 1.9	Adult: Urinary protein >=3.5 g/24 hrs; 4+ proteinuria; Pediatric: Urine P/C (Protein/Creatinine) ratio >1.9	-	-

Urine Protein will have grades 1-3, with

- Grade 1 =1+,
- Grade 2 = 2+ to 3+
- Grade 3 = 4+

Lab Test: Urine RBCs/Blood

CTCAE Term	Grade 1	Grade 2	Grade 3	Grade 4	Grade 5
Hematuria	Asymptomatic; clinical or diagnostic observations only; intervention not indicated	Symptomatic; urinary catheter or bladder irrigation indicated; limiting instrumental ADL	Gross hematuria; transfusion, IV medications, or hospitalization indicated; elective invasive intervention indicated; limiting self care ADL	Life-threatening consequences; urgent invasive intervention indicated	Death

Urine blood will not be CTCAE graded

Lab Test: eGFR or CrCl

CTCAE Term	Grade 1	Grade 2	Grade 3	Grade 4	Grade 5
eGFR decreased/CrCL decreased	eGFR (estimated Glomerular Filtration Rate) or CrCl (creatinine clearance) <lln -="" 60
ml/min/1.73 m2 or proteinuria 2+ present; urine protein/creatinine >0.5</lln>	eGFR or CrCl 59 - 30 ml/min/1.73 m2	eGFR or CrCl 29 - 15 ml/min/1.73 m2	eGFR or CrCl <15 ml/min/1.73 m2; dialysis or renal transplant indicated	Death

Values will be graded using the CTCAE values noted above with Grade 1 - Grade 4 values.

eGFR/CrCL:

Grade 1: < LLN - 60 ml/min/1.73 m2 Grade 2: 30 - < 60 ml/min/1.73 m2 Grade 3: 15 - < 30 ml/min/1.73 m2 Grade 4: < 15 ml/min/1.73

9.7. **Programming Conventions**

- Page orientation, margins, and fonts: Summary tables, listings, and figures will appear in landscape orientation. There should be a 1.0" boundary on the left and right edges. The top and bottom margins are 1.0" for tables and listings, but may vary for figures. Output should be printed in Courier New with a point size of 8.
- Identification of analysis population: Every summary table, listing, and figure will clearly specify the analysis population being summarized/listed. Listings will be prepared for all subjects randomized.
- Group headers: In the summary tables, the group headers will identify the within-group sample size for the indicated analysis population. Of note, the header's sample size does not necessarily equal the number of subjects actually summarized within any given summary module; some subjects in the analysis population may have missing values and thus may not be summarized.
- Suppression of percentages corresponding to null categories: When count data are presented as category frequencies and corresponding percentages, the percent should be suppressed when the count is zero in order to draw attention to the non-zero counts.
- Presentation of sample sizes: Summary modules should indicate, in one way or another, the number of subjects actually contributing to the summary statistics presented in any given summary module. As mentioned above, this may be less than the number of subjects in the analysis population.
 - In the quantitative modules describing continuous variables (and thus presenting sample size, means, and standard deviations), the sample size should be the number of non-missing observations
 - For categorical variables that are presented in frequency tables, the module should present the total count in addition to the count in each category. Percentages should be calculated using this total as the denominator, and the percentage corresponding to the sum itself (that is, 100%) should be presented so as to indicate clearly to a reviewer the method of calculation.
- Sorting: Listings will be sorted by treatment, subject number and date, if applicable. If a listing is sorted in a different manner, it will be indicated on the listing shells.
- General formatting rules: Rounding for all variables will occur only as the last step, immediately prior to presentation in listings, tables, and figures. No intermediate rounding will be performed on derived variables. The standard rounding practice of rounding numbers ending in 0-4 down and numbers ending in 5-9 up will be employed.
- The presentation of numerical values will adhere to the following guidelines (exceptions may be necessary in some circumstances for derived analysis variables to allow readability):
 - Raw measurements will be reported to the number of significant digits as captured electronically or on the eCRFs.
 - Standard deviations will be reported to two decimal places beyond the number of decimal places the original parameter is presented.
 - Means will be reported to the one decimal place beyond the number of decimal places the original parameter is presented.
 - Calculated percentages will be reported with one decimal place.

- Coefficient of variation will be reported to the same number of decimal places as the standard deviation.
- Dates will be formatted as DDMMMYYYY. Partial dates will be presented on data listings as recorded on eCRFs.
- Time will be presented according to the 24-hour clock (HH:MM).
- Verification of Results: All analyses will be subject to formal verification procedures. Specifically, results will be verified utilizing independent programming prior to issuance of the draft statistical report. All documents will be verified by the lead statistician to ensure accuracy and consistency of analyses.

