# 10.2 Appendix 2: Clinical Laboratory Tests

The tests detailed in Table 9 will be performed by the central laboratory.

Protocol-specific requirements for inclusion or exclusion of subjects are detailed in Section 5.

Additional tests may be performed at any time during the trial as determined necessary by the investigator or required by local regulations.

Serology (screening for human immunodeficiency virus, hepatitis B virus, hepatitis C virus) will be done at screening.

Serum pregnancy tests are required for women of childbearing potential (WOCBP) at the time points indicated in the Schedule of Assessments; however, a serum pregnancy test can be done anytime during the trial at the investigator's discretion. Female subjects with exclusively same sex partners may not be required to have pregnancy tests per investigator discretion; confirmation with the medical monitor is required.

Laboratory Assessments	Parameters						
Hematology	Platelet Count         Red blood cell Count         Hemoglobin		Red Blood Cell Indices: Mean Corpuscular Hemoglobin Mean Corpuscular Volume		White blood cell Count with Differential: Neutrophils		
	Hematocrit	lematocrit		%Reticulocytes		Monocytes	
				Eosinophils			
					Basophils		
Clinical Chemistry	Blood urea nitrogen	Potassium		Aspartate Aminotransferase		Total and direct bilirubin	
	Creatinine	Sodium		Alanine Aminotransferase		Total Protein	
	Glucose	Calcium		Alkaline phosphatase		Chloride	
	Bicarbonate						
Routine	Specific gravity						
Urinalysis	pH, glucose, protein, blood, ketones, bilirubin, urobilinogen, nitrite, leukocyte esterase by dipstick						
	Microscopic examination (if blood or protein is abnormal)						

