3.2.2. Clinical Safety Laboratory Assessments

The clinical laboratory tests as listed in the protocol will be performed in accordance with the laboratory manual and the Schedule of Assessments. All results, including repeats, will be included in the laboratory reports. The investigator must review the laboratory report, document this review, and record any clinically relevant changes occurring during the trial in the AE section of the eCRF.

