5.14.3. Clinical Laboratory Assessments

Descriptive summaries of selected (quantitative) clinical laboratory results will be presented by treatment group and study visit. Laboratory values outside the normal range for each systematically collected hematology, blood chemistry, and urinalysis parameter will be identified. Each subject's hematology, blood chemistry, and quantitative urinalysis values will be flagged as "low" (below the lower limit of normal/LLN), "normal" (within the normal range), or "high" (above the upper limit of normal/ULN) relative to the normal ranges of the central laboratory. Each subject's qualitative urinalysis results will be flagged as "normal" or "abnormal." In addition, the severity of laboratory abnormality will be graded based on toxicity criteria specified in Section 9.6 in reference to Common Terminology Criteria for Adverse

Events (CTCAE) Version 5.0. The result of each laboratory test for individual subjects will be presented in a listing with the normal range defined by the central laboratory, the status relative to the normal range, and the toxicity grade.

Shift table will be used to summarize shifts from baseline toxicity grades to greatest (worst) treatment-emergent laboratory toxicity. For hematology and, blood chemistry, and quantitative urinalysis parameters that toxicity grade was not defined, a shift table for each laboratory test will be based on the shift from baseline high/normal/low status to the status of the maximum post-baseline value and the minimum post-baseline value (including test results from unscheduled visits, if any). Similarly, for qualitative urinalysis parameters, shifts from baseline normal/abnormal status to the worst post-baseline status will be summarized.

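### Two grading rules in SAP 9.6 do not work as written: hypokalemia leaves 2.5 mmol/L ungraded and puts 3.0 mmol/L in two grades, and calcium needs an albumin value that the protocol panel does not list

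*SAP*

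**What the plan says.** **Calcium.** Under the test name for corrected serum calcium, SAP 9.6 states "Calcium will have to be corrected for albumin using Payne's formula". The formula is measured calcium plus 0.8 times the difference between 4.0 g/dL and the patient's albumin. A note adds "It should be confirmed with the lab whether or not the correction has already been applied". On the scale the SAP says "The grading is in both directions High and Low. Both directions are graded in 4 categories as Hypercalcemia", and it then lists four hypercalcemia and four hypocalcemia grades in mg/dL.

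**The panel.** Protocol 10.2 states "The tests detailed in Table 9 will be performed by the central laboratory". SAP 3.2.2 ties itself to that list: "The clinical laboratory tests as listed in the protocol will be performed in accordance with the laboratory manual and the Schedule of Assessments".

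**Potassium.** The hypokalemia bullets in SAP 9.6 are "Grade 1 being any values from the LLN to 3.0 mmol/L", then "Grade 3 from >2.5 to 3.0 mmol/L", then Grade 4 for values below 2.5 mmol/L. The CTCAE row above them puts Grade 3 at values below 3.0 down to 2.5.

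**Use.** SAP 5.14.3 tabulates shifts from the baseline grade to the worst treatment-emergent grade. A second kind of table is kept for ungraded parameters; the SAP's wording is "that toxicity grade was not defined, a shift table for each laboratory test will be based on the shift from baseline". Here each subject's category before treatment (high, normal or low) is set against the categories of the highest and lowest later results.

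**The concern.** A grading rule should give each abnormal result exactly one grade, using data the trial collects. The hypokalemia rule fails the first test at its two boundaries. The calcium rule appears to fail the second.

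Both analytes are in the protocol panel, so these are not unused entries. If the bullets are programmed literally, a worst potassium of 2.5 drops out of the grade shift table, although the SAP's own CTCAE row makes it Grade 3. A worst potassium of 3.0 may be reported as Grade 3, although the row makes it Grade 1. For calcium, a programmer without albumin would have to leave the grade blank, grade uncorrected calcium against cut-points meant for corrected calcium, or fall back on another table. The SAP does not say which.

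**Working it through.** The plan states no figure to reproduce here. The check applies the rules to values and compares the rule with the panel.

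**1. Potassium.** Inputs are the SAP 9.6 bullets and the CTCAE row above them. An LLN of 3.5 mmol/L is assumed; it does not affect the two boundaries at issue. Both rules were run from 2.2 to 3.5 mmol/L in steps of 0.1.

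| Potassium (mmol/L) | SAP bullets | CTCAE row |
|---|---|---|
| 2.2 to 2.4 | Grade 4 | Grade 4 |
| **2.5** | **none** | **Grade 3** |
| 2.6 to 2.9 | Grade 3 | Grade 3 |
| **3.0** | **Grade 1 and Grade 3** | **Grade 1** |
| 3.1 to 3.4 | Grade 1 | Grade 1 |

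The CTCAE row also has a Grade 2 for symptomatic cases, which the SAP does not use. Values above 2.5 up to 3.0, together with values below 2.5, exclude 2.5 itself. The Grade 1 and Grade 3 bullets both include 3.0. All other values below the LLN get one grade under either rule.

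The neighbouring low-direction rules close the interval at its lower end: hypocalcemia Grade 3 is 6.0 to <7.0, hypoglycemia Grade 3 is 30 to <40 and hyponatremia Grade 3 is 120 to <125. Only the potassium bullet reverses the pattern, which points to a transcription slip.

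**2. Calcium: is albumin available?** The Table 9 chemistry list is blood urea nitrogen, creatinine, glucose, bicarbonate, potassium, sodium, calcium, AST, ALT, alkaline phosphatase, total and direct bilirubin, total protein and chloride. Albumin is not among them. SAP 9.6 has its own albumin grading entry, but that does not show albumin is collected: the same appendix covers amylase, lipase and CD4 lymphocytes, which are not in Table 9 either.

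**3. Calcium: does the correction matter?** The formula is corrected Ca = measured Ca + 0.8 × (4.0 − albumin). For a measured calcium of 8.2 mg/dL and illustrative albumin values:

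- albumin 3.0 g/dL: 8.2 + 0.8 × 1.0 = 9.0 mg/dL
- albumin 4.0 g/dL: 8.2 + 0.8 × 0 = 8.2 mg/dL (Grade 1 if the LLN is above 8.2)
- albumin 4.5 g/dL: 8.2 + 0.8 × (−0.5) = 7.8 mg/dL (Grade 2, which runs from 7.0 to <8.0)

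A 1 g/dL difference in albumin moves the result by 0.8 mg/dL. The cut-points (8.0, 7.0, 6.0 and 11.5, 12.5, 13.5) are 1.0 mg/dL apart. The specified grade therefore cannot be set without albumin.

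**The case against.** **Calcium may still have a shift table.** A reader might infer that, followed literally, the SAP leaves calcium with none, because a grade is defined and the fallback in 5.14.3 is for ungraded parameters. The documents do not compel that. The graded test is named as corrected serum calcium, so measured calcium, which is what Table 9 collects, can be read as having no defined grade and falling under the high/normal/low table. The text can be read either way. That ambiguity should be settled, but it is not proof of a missing table.

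**The absence of albumin is not certain.** A reader might infer that no corrected value can ever be computed. That goes too far. The hematology part of Table 9 looks damaged in the text read here (the differential lacks lymphocytes), and the laboratory manual is not available. The chemistry part does read as a complete list. The note telling the analyst to check with the laboratory does not solve the problem, since a laboratory correction also needs albumin, but that check might bring the gap to light.

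**Other coverage remains.** SAP 5.14.3 also plans descriptive summaries of selected results, low/normal/high flags for each subject and a listing of every result. Clinically relevant changes are recorded as adverse events (protocol 8.3.4, SAP 3.2.2). A potassium of 2.5 would still be flagged low, assuming an LLN above 2.5. This stands, and it limits the harm.

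**The potassium error is small and likely to be noticed.** The correct boundaries are printed directly above, and SAP 9.7 requires independent programming. Describing 3.0 as over-graded by two grades would also overstate it: the SAP's hypokalemia scale has no Grade 2, so Grades 1 and 3 are adjacent. Even so, independent programmers working from this text could resolve the boundaries differently, so the text itself should be corrected.

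**Conclusion.** Both rules are wrong as written, and the point is a minor SAP correction. The potassium gap and overlap are certain from the text: two boundary values, 2.5 and 3.0 mmol/L, in one analyte. How many results will fall there cannot be estimated from the documents.

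The calcium point rests on Table 9 reading as it does. On that reading, corrected calcium cannot be derived from the protocol-required tests, and the SAP gives no clear alternative.

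The effect stays within the safety laboratory grades and shift tables. Neither analyte appears in the laboratory AESI thresholds of protocol 8.4.6 or the laboratory discontinuation criteria of protocol 7.3, and neither enters any efficacy analysis or the sample size.

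**What to change.** **Potassium (SAP 9.6).** Replace the hypokalemia bullets with Grade 1 = <LLN to 3.0, Grade 3 = 2.5 to <3.0 and Grade 4 = <2.5 mmol/L. Every value below the LLN then has exactly one grade, in line with the printed CTCAE row.

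**Calcium (SAP 9.6 and 5.14.3).** Ask the central laboratory whether it supplies albumin for these samples.

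- If it does, name that source in the SAP and state how a missing albumin is handled.
- If it does not, strike the correction and state that measured calcium is presented in the high/normal/low shift table of 5.14.3.

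The cost is a few words of SAP text and one query to the laboratory, before database lock. Adding albumin to the panel is a different matter: it changes protocol Table 9, not just the SAP, and does nothing for samples already analysed without it.
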